6.3 STUDY INTERVENTION COMPLIANCE

The GOALS platform contains built-in software to track compliance with intervention protocols. Specifically, the platform tracks the number of times they've logged into the system, the time spent in the system, the number of lessons viewed, workbook pages completed, self-monitoring, and communication with the lifestyle coach. The lifestyle coach will be instructed to reach out to participants if they have not logged into the system for two consecutive weeks to query challenges and provide encouragement to re-engage.

7 STUDY INTERVENTION DISCONTINUATION AND PARTICIPANT DISCONTINUATION/WITHDRAWAL

7.1 DISCONTINUATION/WITHDRAWAL FROM THE STUDY INTERVENTION

Participants may withdraw voluntarily from the study at any time by submitting a formal request to the study PI. We will still use data collected before the voluntary withdrawal. The PI may discontinue a study participant if there are changes to their eligibility status, including becoming pregnant or using medications that affect weight. Any new clinically relevant finding will be reported as an adverse event (AE).

The data to be collected at the time of study intervention discontinuation will include the following:

- Reasons for discontinuation
- Timing of discontinuation
- Adverse event details (if applicable)
- Follow-up data (if applicable)
- Documentation on each participant's last available data point(s), including sleep health, diet, physical activity measurements, weight, and any other relevant outcome measures

7.2 PARTICIPANT DISCONTINUATION/WITHDRAWAL FROM THE STUDY

An investigator may discontinue or withdraw a participant from the study for the following reasons:

- Pregnancy
- If any clinical adverse event (AE) or other medical condition or situation occurs such that continued participation in the study would not be in the best interest of the participant
- If the participant meets an exclusion criterion (either newly developed or not previously recognized) that precludes further study participation

The reason for participant discontinuation or withdrawal from the study will be recorded on the study discontinuation form. Subjects who sign the informed consent form and are randomized but do not receive the study intervention may be replaced. Subjects who sign the informed consent form, are randomized and receive the study intervention, and subsequently withdraw, or are withdrawn or discontinued from the study not be replaced.

8 STUDY ASSESSMENTS AND PROCEDURES

8.1 PRELIMINARY EFFICACY AND COVARIATE ASSESSMENTS

Assessments will be conducted at baseline (Week 0) prior to randomization and immediately after completion of the intervention (Week 16). Assessments will be conducted by a research team member in the PHB lab. Assessments should take 1-2 hours to complete. Participants will receive pre-visit instructions 3 days before their scheduled in-person visits. Assessments will consist of the following:

- Height, weight & waist circumference: Height will be measured with a stadiometer at study enrollment (T0). Weight will be measured using a calibrated digital scale. Women will be measured in street clothes without shoes.
- Demographic information: Age, race, ethnicity, income, educational background, employment status, health insurance status, marital status, family composition (e.g., number of adults and children in the household), smoking status, and current alcohol use.
- Mental wellness: Participants will complete the Edinburgh Postnatal Depression Scale to measure the frequency of depressive symptoms. The Perceived Stress Scale will be used to measure perceived stress.
- Infant sleep and eating: The Brief Infant Sleep Questionnaire - Revised (BISQ) Short Form will be used to assess infant sleep patterns. The infant feeding questionnaire to assessing infant eating patterns.
- Social determinants of health: The Barkin Index of Maternal Functioning (BIMF) is a 20-item self-report measure that was designed to assess overall functioning in the context of new motherhood. The EveryONE project social determinants of health screener to identify the social needs of participants.
- Social support: The RAND social support survey helps identify the types of support available to participants.
- Diet: The study will utilize the Automated Self-Administered 24-hour (ASA24) Dietary Recall System to collect information about what participants ate in the prior 24 hours
- Physical activity and sleep: Following the in-person visit, we will give participants an Actigraph Link, which is a research-grade activity monitor, to wear on their wrist for 7

days to assess their physical activity and sleep patterns. The Actigraph will be used solely for the purposes of physical activity and sleep measurement. This study will not test the efficacy of the device. During the 7 day assessment period, participants will complete a sleep diary to help us better interpret the monitor data. After the 7 day assessment, participants will mail the Actigraph and diary back to us in a pre-paid postage envelope. Participants will also complete a modified SASS-Y and PAQ questionnaires.

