1.2 SCHEMA

1.3 SCHEDULE OF ACTIVITIES (SOA)

Procedures	Screening, Day -7 to -1	Enrollment/Baseline, Day -7 to -1	Day 1	Final Assessment, Day 112+8
Eligibility determination	X			
Informed consent		X		
Randomization		X		
Administer the intervention			X-----X	
Outcome Assessment				
Feasibility indicators		X		
Acceptability indicators			X-----X	
Height and Weight	X	X		X
Descriptive characteristics				
Demographics	X	X		
Infant Feeding and Behavior		X		X
Mental Wellness		X		X

Treatment Expectations		X		
Weight Goals		X		
Social Support		X		X
Social Determinants of Health		X		
Health Behaviors				
Physical activity	X	X		X
Diet		X		X
Sleep	X	X		X

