4 STUDY DESIGN

4.1 OVERALL DESIGN

This study will use a single-blind, parallel-arm RCT design. Participants will be randomized at a 1:1 ratio to Sleep GOALS intervention (n=20) or an education control group (n=20).

Sleep GOALS: We anticipate Sleep GOALS will be a 16-week intervention. However, the results of Aim 1 will determine the intervention length and core content. We will use a protocol [name] and colleagues developed to adapt TSC to an online format and integrate it with the GOALS lifestyle intervention.^{6,7} Briefly, in-person delivery of TSC has 3 components: 1) delivery of the core content, 2) providing tailored feedback, and 3) providing motivation and support. We will adapt the first component to an online format with 15-to-20-minute informational videos. The participants will view the material at their convenience, with new videos available weekly. The GOALS software will send weekly automated email reminders to review the new session materials. We will use a lifestyle coach to adapt the 2nd and 3rd components. Evaluating patient perspectives on the original GOALS lifestyle intervention found individualized lifestyle coaching, encouragement, and accountability helpful.⁸ The coach will be a master's level student in a health-related program (e.g., physical activity and health promotion, nutrition and dietetics, etc.) with experience in weight-management counseling. As described in Aim 1, the coach will assist with developing Sleep GOALS to familiarize them with the intervention content. However, the coach will complete a 2-day training workshop using a similar training format as the GOALS Lifestyle intervention.⁷ The coach will help participants develop an individualized sleep treatment plan based on their baseline sleep assessment. For example, coaches will encourage participants to document challenges for sleep (e.g., infant sleep, lack of partner support) and identify one treatment strategy they deem feasible to implement each week. The coach will monitor participant progress and engagement weekly to revise the sleep treatment plan, diet, and activity as needed. Coaches will provide personalized feedback and encourage accountability and re-engagement through a secure messaging system in the Sleep GOALS platform.⁷ The PI will randomly check coach-participant communication weekly to ensure intervention fidelity. IF NECESSARY, the PI will meet with the coaches weekly to discuss challenges and participant communication. Lastly, participants will be given a wireless scale for self-monitoring weight and a Fitbit for self-monitoring sleep (daily minutes) and physical activity (daily steps, minutes). The Fitbit dashboard also allows participants to track dietary calories. Participants will receive instructions on how to sync the scale and Fitbit data with the Sleep GOALS platform. Participants will be asked to weigh themselves in light clothing at least once weekly.⁹

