6.2 MEASURES TO MINIMIZE BIAS: RANDOMIZATION AND BLINDING

We will use REDCap to generate the randomization plan. We will use blocked randomization (blocks of 4) to ensure balanced intervention groups. The randomization plan results will be maintained in REDCap and only accessible by a lifestyle coach who will support participants in the intervention arm (further detailed below) but is not directly involved with data collection. Assignment allocation will be concealed from participants until after the baseline assessments. Investigators will remain blinded until post-intervention data collection is complete.

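### The 7-day baseline Actigraph recording starts after a visit set for Day -7 to -1, so only the earliest visit day leaves room to finish it before randomization and Day 1

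*Combined protocol and SAP*

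**What the plan says.** Section 8.1 lists wrist actigraphy among the assessments made at baseline and after the intervention. On its start it says: "Following the in-person visit, we will give participants an Actigraph Link". Wear lasts 7 days, with a diary alongside: "During the 7 day assessment period, participants will complete a sleep diary". Then: "After the 7 day assessment, participants will mail the Actigraph and diary back to us in a pre-paid postage envelope".

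The Schedule of Activities (1.3) has a column headed "Enrollment/Baseline, Day -7 to -1". It holds the marks for consent, randomization, physical activity and sleep. The intervention runs from Day 1. Screening carries the same dates as baseline.

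On order, 8.1 states: "Assessments will be conducted at baseline (Week 0) prior to randomization". The synopsis and section 10.1.2.1 agree. Section 6.2 adds: "Assignment allocation will be concealed from participants until after the baseline assessments".

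No section says that the 7-day recording must be finished, or the device returned, before randomization, disclosure of allocation or Day 1.

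Section 9.4.2 treats change in sleep, diet and physical activity as exploratory and intends it to inform power calculations. Section 9.2 plans estimates of the variability of those changes for the same purpose.

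**The concern.** A recording that begins after the visit and lasts 7 days needs 7 clear days before anything related to treatment. The window is itself only 7 days long, and randomization has to fit into it as well.

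Once allocation is disclosed, both arms receive material on sleep and activity: brochures for controls, and videos, a coach and a self-monitoring tracker for the intervention arm. Wear days after that point are no longer baseline, and their number would differ between participants with the day of the visit. The change from baseline, and its variability, would then mix clean and partly treated starting values. These are the figures that the larger trial is meant to use.

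**Working it through.** **Inputs.** Wear of 7 days, starting after the visit (8.1). Visit and randomization within Day -7 to -1, intervention from Day 1, final assessment at Day 112+8, read here as Day 112 to 120 (1.3). Participant duration of 18 to 20 weeks (synopsis). The protocol does not say whether wear starts on the visit day or the next day, or whether the calendar has a Day 0, so all four combinations are shown.

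**The plan's own duration.** Days before Day 1, plus day of final visit, plus 7 days of final wear:

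- Day -7 visit: 7 + 112 + 7 = 126 days = 18.0 weeks, up to 7 + 120 + 7 = 134 days = 19.1 weeks. Both lie within the stated range.
- Day -1 visit: 1 + 112 + 7 = 120 days = 17.1 weeks, below the range, up to 1 + 120 + 7 = 128 days = 18.3 weeks, within it.

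**Overlap.** For a visit on Day -k, the number of wear days on or after Day 1 is max(0, 7 - k + s - z). Here s = 1 if wear starts the next day (otherwise 0), and z = 1 if a Day 0 is counted (otherwise 0).

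| Variant | -7 | -6 | -5 | -4 | -3 | -2 | -1 | Mean of 7 days |
|---|---|---|---|---|---|---|---|---|
| No Day 0, same-day start | 0 | 1 | 2 | 3 | 4 | 5 | 6 | 21/7 = 3.0 (43%) |
| No Day 0, next-day start | 1 | 2 | 3 | 4 | 5 | 6 | 7 | 28/7 = 4.0 (57%) |
| Day 0, same-day start | 0 | 0 | 1 | 2 | 3 | 4 | 5 | 15/7 = 2.1 (31%) |
| Day 0, next-day start | 0 | 1 | 2 | 3 | 4 | 5 | 6 | 21/7 = 3.0 (43%) |

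The means assume visits spread evenly over the seven days.

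**Can every statement be met?** Randomization must follow the wear and still fall within Day -7 to -1. A Day -7 visit with same-day start gives wear on Days -7 to -1, so randomization fits at the end of Day -1. The other zeros in the table (Day -6 with same-day start, or Day -7 with next-day start, both with a Day 0) have wear ending on Day 0, which puts randomization outside its window. So one visit day and one start rule satisfy the text and the schedule together.

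**The case against.** The strongest reply is that the protocol states the right order three times (synopsis, 8.1, 10.1.2.1) and conceals allocation until baseline is done. The schedule column is a window that gives no order within it. A 7-day window for a 7-day recording may simply mean a visit on Day -7, and the stated duration fits that reading better than a Day -1 visit. Much of this stands, and it rules out several stronger readings:

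- *Most baseline wear follows allocation.* A reader might infer this from the randomization mark in the baseline column. It would need randomization at the visit itself, which the documents do not say and the three statements on order contradict.
- *Most baseline wear falls on or after Day 1.* Under an even spread, the share exceeds half in only one of the four variants, and the documents give no distribution of visit days.
- *No visit day gives a clean baseline.* This could be argued from the shared screening window and the pre-visit instructions sent 3 days ahead. It needs those instructions to follow screening, which is not stated.
- *Baseline adjustment is compromised.* No analysis adjusted for baseline sleep or activity is planned; section 9.4.1 is descriptive.
- *Change is biased toward zero.* Attenuation in the intervention arm is plausible, but the documents offer nothing to size it.
- *The coach's plan rests on late data.* Section 4.1 says: "The coach will help participants develop an individualized sleep treatment plan based on their baseline sleep assessment". It does not identify that assessment as actigraphy, and questionnaires are also collected.

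The reply does not remove the conflict. The schedule allows visits up to Day -1, and for those the statements on order and the window cannot both be kept. A late final visit also brings a Day -1 visit back within the stated duration, so the duration does not exclude it.

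**Conclusion.** The concern holds as a conflict between the schedule and the stated order of assessments. A visit on Day -6 to -1, which the schedule permits, either pushes wear into the intervention period or prevents randomization from both following the wear and staying in its window. Full compliance is possible, but only with a Day -7 visit and same-day wear.

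For one participant the overlap runs from 0 to 7 of 7 wear days. The average of 31% to 57% rests on an assumed even spread of visits and on the two unstated conventions (wear start and Day 0). It is not an estimate of what will happen.

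The effect is confined to exploratory change and variability in actigraphy- and diary-based sleep and physical activity. Weight, postpartum weight retention, feasibility and acceptability are unaffected. The change should be made because these exploratory figures are intended for the next trial's power calculations and the repair is cheap.

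**What to change.** 1. Schedule the baseline visit at least 8 days before Day 1, and move the screening window earlier to match. Otherwise a Day -8 visit would precede all of screening.
2. Give randomization its own schedule column, with randomization and disclosure of allocation only after the 7 wear days are complete. State whether wear starts on the visit day or the next day, and whether there is a Day 0.
3. Exclude from the baseline value any wear day on or after disclosure of allocation, and report how many days each participant contributes.

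The cost is schedule wording and about one more week before Day 1. From a Day -8 visit to the end of final wear is at most 8 + 120 + 7 = 135 days = 19.3 weeks, within the stated 18 to 20. The 20-week limit (140 days) leaves 140 - 120 - 7 = 13 days before Day 1, so there is some slack beyond Day -8. With a next-day start and no Day 0, some of it is needed, because a Day -8 visit then leaves no free day between the end of wear and Day 1. Rule 3 may leave some participants with fewer than 7 baseline days.

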8.2 ADVERSE EVENTS AND SERIOUS ADVERSE EVENTS

8.2.1 DEFINITION OF ADVERSE EVENTS (AE)

Adverse event means any untoward medical occurrence associated with the use of an intervention in humans, whether or not considered intervention-related (21 CFR 312.32 (a)).

8.2.2 DEFINITION OF SERIOUS ADVERSE EVENTS (SAE)

An adverse event (AE) or suspected adverse reaction is considered "serious" if, in the view of either the investigator or sponsor, it results in any of the following outcomes: death, a life-threatening adverse event, inpatient hospitalization or prolongation of existing hospitalization, a persistent or significant incapacity or substantial disruption of the ability to conduct normal life functions. Important medical events that may not result in death, be life-threatening, or require hospitalization may be considered serious when, based on appropriate medical judgment, they may jeopardize the participant and require medical or surgical intervention to prevent one of the outcomes listed in this definition. Examples of such medical events include allergic bronchospasm requiring intensive treatment in an emergency room or at home, blood dyscrasias or convulsions that do not result in inpatient hospitalization or the development of drug dependency or drug abuse.

8.2.3 CLASSIFICATION OF AN ADVERSE EVENT

8.2.3.1 SEVERITY OF EVENT

The following guidelines will be used to describe the severity of adverse events (AEs) not included in the protocol-defined grading system.

- **Mild** – Events require minimal or no treatment and do not interfere with the participant's daily activities.
- **Moderate** – Events result in low inconvenience or concern with the therapeutic measures. Moderate events may cause some interference with functioning.
- **Severe** – Events interrupt a participant's usual daily activity and may require systemic drug therapy or other treatment. Severe events are usually potentially life-threatening or incapacitating. Of note, the term "severe" does not necessarily equate to "serious."

8.2.3.2 RELATIONSHIP TO STUDY INTERVENTION

All adverse events (AEs) must have their relationship to study intervention assessed by the PI, who examines and evaluates the participant based on temporal relationship and their judgment. The degree of certainty about causality will be graded using the categories below. In a clinical trial, the study product must always be suspect.

- **Related** – The AE is known to occur with the study intervention, there is a reasonable possibility that the study intervention caused the AE, or there is a temporal relationship between the study intervention and the event. Reasonable possibility means that there is evidence to suggest a causal relationship between the study intervention and the AE.
- **Not Related** – There is not a reasonable possibility that the administration of the study intervention caused the event, there is no temporal relationship between the study intervention and event onset, or an alternate etiology has been established.

8.2.3.3 EXPECTEDNESS

The principal investigator will determine whether an adverse event (AE) is expected or unexpected. An AE will be considered unexpected if the nature, severity, or frequency of the event is not consistent with the risk information previously described for the study intervention.

8.2.4 TIME PERIOD AND FREQUENCY FOR EVENT ASSESSMENT AND FOLLOW-UP

The occurrence of an adverse event (AE) or serious adverse event (SAE) may come to the attention of study personnel during study visits, community with the lifestyle coach during the intervention, and interviews. We will record all reportable events with start dates occurring any time after informed consent is obtained until 7 days (for non-serious AEs) or 30 days (for SAEs) after the last day of study participation. We will assess and document AEs and SAEs at each study visits, inquiring about the occurrence of AEs and SAEs since the last visit, with a focus on any issues related to sleep, diet, physical activity, or weight loss. We will follow up on all events for outcome information until resolution or stabilization.

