2.3 RISK/BENEFIT ASSESSMENT

2.3.1 KNOWN POTENTIAL RISKS

We categorize the frequency of possible risk using the following categories: likely (occurs in >25% of people), common (occurs in 10-25% of people), infrequent (occurs in 1-10% of people), and rare (occurs in <1% of people). We will monitor the risk related to the intervention and data collection.

Intervention-Related Risk:

- The recommended physical activity may cause muscle soreness or fatigue (likely). There is the possibility that the following occurs during exercise: injury of a joint or muscle (common), broken bones (rare), falls from exercise equipment (infrequent). There is also the possibility of aggravating pre-existing problems (common), shortness of breath (common), abnormal blood pressure (common), fainting (rare), disorders of heart rhythm (rare), heart attack, stroke, or even death (rare).
- The recommended weight loss may cause constipation (common) and dizziness upon standing (common). Rapid weight loss increases the chances of developing or enlarging gallstones (rare). Other risks include hypoglycemia (infrequent), light-headedness or weakness (common), and hunger (likely).
- Wearing the wrist-worn activity monitor may cause some discomfort in the form of skin irritation (infrequent).

Data Collection Related Risk:

- The potential risks of participating in this study include discomfort (rare) from answering questions, disclosure of postpartum depression or child neglect/abuse (infrequent), and breach of confidentiality (rare).

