3 OBJECTIVES AND ENDPOINTS

Primary Outcomes: The primary outcomes are feasibility and acceptability factors relevant to conducting a subsequent efficacy trial, including the feasibility of recruitment, retention, and engagement (Table 5). To determine acceptability, we will ask participants to complete a modified Acceptability and Feasibility Questionnaire¹ post-intervention. The questionnaire asks participants to provide answers on a 5-point scale (1=*don't agree at all* to 5=*totally agree*) to 39 items about the intervention delivery (e.g., logical, understandable), curricula (e.g., was it logical, relevant, instructive), action plans (e.g., useful, easy to follow), and intervention platform (e.g., user friendly). We will also ask about the coaches' effectiveness, overall satisfaction with the intervention, and the likelihood they would recommend it to a friend. Items with an average score of <4 will be flagged for refinement.

We will then conduct 60-minute semi-structured interviews with participants and coaches. The interviews will take place in person (PHB lab) or by video chat at the participant's preference. We will ask participants whether the content was understandable, the recommendations achievable, and what adaptations are necessary to improve low-scoring items. We will ask the lifestyle coach to discuss their experience and provide suggestions for improving the delivery of the material and their workflow. All interviews will be audio-recorded and transcribed by Qual EASE for qualitative analysis. The feedback will be used to refine the intervention's content delivery, coach's workflow, and training manual. Participants will receive \$50 after each assessments and intervention participants will receive a \$25 honorarium for completing the post-intervention interview.

Secondary Outcomes: *Weight* will be measured with a digital scale, with the participant wearing light clothing and no shoes at baseline and post-intervention. We will estimate PWR as the difference in measured weight at post-intervention and self-reported pre-pregnancy weight.

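### Sleep GOALS participants have more routes by which an adverse event can be noticed than controls do, and the protocol neither records the route nor limits by-arm counts to the one inquiry both arms share.

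*Combined protocol and SAP*

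**What the plan says.** Section 8.2.4 names three ways in which an event may reach study staff: "study visits, community with the lifestyle coach during the intervention, and interviews" (the second evidently means communication with the coach). It then sets one systematic procedure: "We will assess and document AEs and SAEs at each study visits, inquiring about the occurrence of AEs and SAEs since the last visit". Section 8.1 and the Schedule of Activities (Section 1.3) put assessments at baseline, before randomization, and at Week 16. Each arm therefore has exactly one solicited inquiry after randomization, covering about 16 weeks.

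The other two routes are not shared equally:

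- **Coach.** Section 6.2 describes "a lifestyle coach who will support participants in the intervention arm". Under Section 4.1 the coach reviews progress weekly. Sections 5.4 and 6.3 have the coach contact anyone who has not logged in for two weeks.
- **Interview.** Section 3 describes interviews about intervention content and gives intervention participants an honorarium "for completing the post-intervention interview". It does not say outright that controls are not interviewed.
- **Controls.** Section 4.1 gives them brochures. No contact is scheduled between baseline and Week 16.

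On the use of the data, Section 2.3.1 states "We will monitor the risk related to the intervention and data collection". Section 8.2.3.3 calls an event unexpected if "the nature, severity, or frequency of the event is not consistent with the risk information" already described for the intervention. Section 10.1.2.1 has the PI review data bi-monthly for safety issues. Section 9 contains no adverse-event analysis, and Section 9.1 rules out formal hypothesis testing. Nothing asks for the source of an event to be recorded.

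**The concern.** When one arm has more contact with staff, it has more chances to report an event. The likely and common risks in Section 2.3.1 include muscle soreness, fatigue, dizziness and light-headedness. These are minor and plausibly forgotten by a visit up to 16 weeks later, but easily mentioned to a coach in the week they occur. If so, a by-arm table would show more events under Sleep GOALS even where the intervention caused none, and a reader could not separate extra risk from extra contact.

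There is also an effect on monitoring. A control participant's event has no scheduled route to the PI before that participant's Week 16 visit, whereas a Sleep GOALS event can surface in any week. The bi-monthly review would thus see the two arms with different delays. Since the pilot is meant to refine the conduct of a larger trial, an uneven procedure could be carried forward.

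**Working it through.** **The plan's own figures.** The only design figures are the confidence-interval widths in Section 9.2: 0.31 for 40 participants and 0.44 for 20. A Wald 95% interval has width 2 × 1.96 × √(p(1−p)/n). At p = 0.5 this gives 0.3099 for n = 40 and 0.4383 for n = 20, so both reproduce. The protocol gives no figure for adverse events.

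**Model.** Let

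- q = true risk of a given event, set equal in the two arms;
- r = share of events captured by the Week 16 inquiry, the same in both arms;
- c = share of the events missed at Week 16 that the coach or interview picks up, Sleep GOALS only.

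The recorded risk is q·r in controls and q·[1 − (1−r)(1−c)] in Sleep GOALS. The ratio is 1 + (1−r)c/r, which does not depend on q. The protocol gives neither r nor c; both are assumptions, shown over a range.

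| r | c = 0 | c = 0.25 | c = 0.5 | c = 0.75 |
|---|---|---|---|---|
| 0.4 | 1.00 | 1.375 | 1.75 | 2.125 |
| 0.6 | 1.00 | 1.17 | 1.33 | 1.50 |
| 0.8 | 1.00 | 1.06 | 1.125 | 1.19 |
| 1.0 | 1.00 | 1.00 | 1.00 | 1.00 |

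For r = 0.4 and c = 0.5, capture is 1 − 0.6 × 0.5 = 0.70 against 0.40, a ratio of 1.75. More extreme inputs go further: r = 0.2 and c = 0.7 give 0.76/0.20 = 3.8.

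**In participants.** Take q = 0.25, the boundary between common and likely in Section 2.3.1; applying it to both arms is an assumption. There are then 5 true cases per arm of 20. With r = 0.4 and c = 0.5, 2.0 are recorded in controls and 3.5 in Sleep GOALS. With r = 0.6 and c = 0.5, it is 3.0 and 4.0.

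**Against sampling error.** The gap in proportions is q(1−r)c = 0.25 × 0.6 × 0.5 = 0.075. The 95% half-width for a difference between two arms of 20 is 1.96 × √(2p(1−p)/20): 0.268 at p = 0.25 and 0.310 at p = 0.5. The largest gap in the grid at q = 0.5 is 0.5 × 0.6 × 0.75 = 0.225, still inside 0.310.

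**Engagement.** If pick-up rose in proportion to engagement e (c = 0.5e, r = 0.6), the ratio would be 1.00, 1.17, 1.27 and 1.33 at e = 0, 0.5, 0.8 and 1.0. The protocol does not fix that direction: two weeks without a login triggers coach messages and check-in calls, so a disengaged participant may get more direct contact.

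**After the fix.** If the by-arm summary uses only the shared inquiry, c = 0 in both arms and the ratio is 1.00 at equal true risk and equal recall.

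**The case against.** The strongest reply is that nothing planned is harmed. The endpoints are feasibility, acceptability, weight and weight retention, and Section 9 compares no event rates. The one systematic inquiry is already identical in both arms, and no section tells the coach to ask about adverse events. Both model inputs are assumed. The headline case also overstates the effect if an event worth telling the coach is one the participant would recall anyway, since pick-up of missed events would then be lower. All of this stands, and it limits the point to monitoring and the reading of counts.

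Four stronger readings are tempting, and the documents do not support them:

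- *Recorded rates must differ by arm.* Only opportunity must differ; with r = 1 or c = 0 the counts agree.
- *Detection falls as engagement falls.* The outreach rules in Sections 5.4 and 6.3 leave the direction open.
- *Poor detection in controls corrupts the expectedness judgement.* Section 8.2.3.3 compares an event with the risks described for the intervention, not with the control arm.
- *The interview is certainly confined to one arm.* That is an inference from its content and honorarium. It also comes after the intervention, so it adds no coverage during the 16 weeks.

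It can also be said that tagging an event as coach-reported reveals the arm to a PI whom Section 6.2 keeps blinded. This carries little weight, because Section 4.1 already has the PI check coach messages weekly.

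**Conclusion.** The point holds in a limited form. Opportunity to detect adverse events is unequal by design, and no section corrects for it. Whether recorded counts become unequal depends on two unknowns, Week 16 recall and coach or interview pick-up. Over the range tabulated, the ratio at equal true risk runs from 1.00 to 2.125, with 1.75 at recall 0.4 and pick-up 0.5. Within this model any bias is towards more events in Sleep GOALS. In the 1.75 case, at a true risk of 0.25, the gap is 1.5 participants per arm, small beside sampling error at 20 per arm. That makes it hard to see in the data but does not remove it.

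A reader might infer that the control arm is useless as a safety comparator. The documents do not support that: the Week 16 inquiry is common to both arms and gives a comparable count if it is kept separate. What is at stake is how by-arm counts are read and how soon control events reach the PI, not any stated analysis.

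**What to change.** In Section 8.2.4:

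1. Record the source of each event (visit, coach, interview, other), allowing more than one.
2. Put the same structured questions to every participant at Week 16, including about events already reported elsewhere.
3. Base any by-arm event summary only on events elicited by that shared inquiry, and list coach- and interview-reported events separately so that no safety information is lost.

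Steps 1 and 2 need care. If only the first source were kept, events told to the coach would drop out of the Sleep GOALS count. With r = 0.4, c = 0.5 and independent reporting, that count would be 0.4 × (1 − 0.5) = 0.20 against 0.40 in controls, reversing the bias. The summary also still assumes equal recall in the two arms. The cost is one field in the existing REDCap database and a fixed question set.

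Optionally, send both arms an identical short REDCap adverse-event questionnaire at the same fixed times during the 16 weeks, independent of the coach. This would shorten recall and give controls a scheduled route before Week 16. Its downsides are a little participant time, added contact in a control arm chosen to be inert, which could slightly affect retention (a primary outcome), and more events for the PI to assess and report to the sponsor within the 24 hours set in Section 8.2.5.
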